3.2. Study Outcome Measures

3.2.1. Primary Outcome Measures

Safety

- Occurrence of vaccine-related SAEs from the time of the first study vaccination (M-001 or placebo) until end of first passive surveillance period
- Occurrence of NOCIs from the time of the first study vaccination (M-001 or placebo) until end of first passive surveillance period
- Occurrence of solicited injection site and systemic reactogenicity events on the day of each study vaccination through 8 days after each study vaccination (day of the vaccination inclusive)
- Occurrence of unsolicited AEs from the time of first study vaccination through 22 days after each study vaccination (day of the vaccination inclusive)
- Occurrence of all SAEs, regardless of the assessment of relatedness, from the time of receiving the first M-001 study vaccination until end of first passive surveillance period

Clinical Efficacy

- Percentage of either qRT-PCR or culture-confirmed influenza cases in the M-001 experimental group vs. placebo (during period of ≥ 15 days after the second vaccination until epidemiological levels of influenza are low as defined by the medical director) caused by any influenza A or B virus in association with a protocol defined Influenza Like Illness (ILI is defined as symptoms that include one of the respiratory symptoms (sore throat, cough, sputum production, nasal discharge or congestion, wheezing or difficult breathing) and at least one additional systemic symptom [fever (oral temperature $>37.2^{\circ}\text{C}$ for age 50-59, or $>36.7^{\circ}\text{C}$ for age 60 or more, or increased $\geq 1.3^{\circ}\text{C}$ from baseline), headache, myalgia and/or arthralgia, chills, and fatigue (tiredness for at least 12 hours)]. NP or combined nasal and throat swab will be collected from participants who meet the ILI definition within 24 hours from ILI being reported to or identified by study personnel for qRT-PCR analysis of influenza A and/or B virus. PCR confirmed samples will be further analyzed for culture confirmation.

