All serious adverse events (SAEs) and new onset of chronic medical illness (NOCIs) will be collected from Day 0 until the end of the participation in the trial by the subject.

Adverse events of special interest (AESIs) will be captured as SAEs. These include new onset of Guillain-Barré Syndrome (GBS), Bell's Palsy, encephalitis / myelitis, optic neuritis, Stevens-Johnson Syndrome, and toxic epidermal necrolysis.

Passive efficacy surveillance: Following randomization and vaccinations, subjects will be instructed to contact the site if they experience symptoms of a respiratory illness or influenza-like illness during the annual surveillance periods defined as from Day 14 after second vaccination day until 15 May of the following year.

Active efficacy surveillance will be performed from November 15th (in Season 1) or from December 1st (in Season 2) until the week of 30 March the following year, the most likely period of influenza virus circulation in the Northern Hemisphere.

The participants will be contacted by a dedicated study staff up to twice a week between approximately November 15th through March 31st.

Participants will be contacted as described above by non-site study staff to monitor for influenza-like illness (ILI).; participants identified this way as potentially having ILI will be followed up by relevant study site personnel to confirm if the participant's symptoms and signs meet study ILI definition.

ILI is NOT to be understood as condition caused specifically by influenza virus. The etiology of ILI may be very different, and only after analysis of swabs taken from subjects, the presence or absence of influenza virus in swab sample can be determined. Hence, even if it is suspected that ILI is caused by e.g. a bacteria, or by some other virus than influenza virus, such ILI remains valid reason for swab collection, also because in some cases there may be a superinfection or parallel infection with influenza virus.

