Protocol defined ILI end date is the date when for at least 24 hours ILI symptoms are no longer present. Of note, some symptoms may persist after ILI for a long time, but the duration of ILI is to be determined by presence of symptoms of ILI understood as active disease, or “influenza symptom”, contrary to symptoms being part of an underlying chronic condition (e.g. COPD, arthritis), and contrary to chronic complications and/or sequelae of the ILI. When no clear end of ILI can be observed, the PI is requested to make rational judgment and determine the ILI end date based on available data and his/her experience. It is expected, that normally, ILI should not last longer than 2-3 weeks, and in case of suspected overlapping new infection, the two infection episodes should be recognized by PI as separate ILI cases.

Laboratory testing for the confirmation of influenza:

All NP/nasal and throat swab specimens will be submitted for analysis by polymerase chain reaction (qRT-PCR), and when the result is found positive, and if there is a sufficient content of viruses (as determined by Ct value ≤ 35)” [Ct= cycle threshold] another aliquot from such specimen will be also examined by culture confirmation test. Typing and subtyping of the influenza virus will be performed with PCR based method.

Optional test: Positive cultures samples will be stored and may undergo additional testing in the future (subtyping or strain identification, utilizing genetic sequencing and antigenic analysis using hemagglutination inhibition [HAI] against a panel of known standard ferret reference antisera to different viral strains) to further determine the breadth of protection provided by M-001.

Out of study influenza infection confirmation: in cases when no swab collection was performed within study framework, but valid, relevant external medical documentation exists confirming recent or ongoing influenza infection (laboratory confirmation – PCR, culture or serology - IgM antibodies), such medical documentation will be subject to sponsor’s approval as surrogate proofs of influenza infection, and if approved as valid, may be taken into account for exploratory analyzes. Details of exploratory analyzes will be defined in statistical analysis plan.

7.4. Safety Follow Up Visit, Visit 4, Day 202: Phone Call/ Electronic Communication (180 days [+/-14 days] post last study vaccination day)

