Subjects will be contacted by phone or electronic communication (e.g., email, text message) to query for safety events. In case follow-up contact is needed based on the responses, subjects will be asked to provide further details to the follow-up by phone. AEs limited to NOCIs and SAEs that have occurred since the previous visit will be solicited. Based on the information, subjects may be asked to return to the clinic for evaluation.

7.5. Follow Up Period for Efficacy Season 2

Passive surveillance will take place starting 14 days after the second injection and until May 15, 2020.

Active surveillance for cohort 2 will take place between December 1st, 2019 and March 31, 2020. During this period, the dedicated study staff will contact the participants up to twice a week to monitor for ILI symptoms as detailed above in 7.3. (Follow up calls in season 2019/20 will be for participants in cohort 2 only).

As of the end of the season 1, the follow up for Cohort 1 subjects in season 2019/2020 is not planned and participation of all Cohort 1 subjects will be assumed as completed with the end of Season 1, i.e. the latest on May 15th except for cases defined elsewhere (e.g. ongoing ILI, SAE follow-up).

7.6. Follow Up Period for Efficacy Season 3

Season 3 is not planned and is not encompassed by this study protocol.

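### The primary SAE and NOCI outcomes run to 15 May, but the last scheduled safety query is Visit 4 and the SAP tables stop 30 days after it

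*Protocol*

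**What the plan says.** Protocol 3.2.1 lists among the primary safety outcomes "Occurrence of NOCIs from the time of the first study vaccination (M-001 or placebo) until end of first passive surveillance period" and "Occurrence of vaccine-related SAEs from the time of the first study vaccination (M-001 or placebo) until end of first passive surveillance period". A further primary outcome, all SAEs regardless of relatedness, has the same end point, and SAP 3.1 sets the same window. Protocol 7.5 dates that end for Cohort 2: "Passive surveillance will take place starting 14 days after the second injection and until May 15, 2020". For Cohort 1 it states that "participation of all Cohort 1 subjects will be assumed as completed with the end of Season 1, i.e. the latest on May 15th". Protocol 7.3 lets the medical director instruct otherwise.

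The schedules of events (Protocol Tables 3 and 4) tick SAEs, AESIs and NOCIs at Visits 1, 2 and 4, plus Visit 3 for Cohort 2. Protocol 7.4 describes Visit 4 as "Phone Call/ Electronic Communication (180 days [+/-14 days] post last study vaccination day" and says of its content that "AEs limited to NOCIs and SAEs that have occurred since the previous visit will be solicited".

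Protocol 7.3 says SAEs and NOCIs "will be collected from Day 0 until the end of the participation in the trial by the subject", and a row in Tables 3 and 4 allows collection at any time. Neither attaches a contact to that rule. On the active surveillance calls, 7.3 says: "Participants will be contacted as described above by non-site study staff to monitor for influenza-like illness (ILI". Passive surveillance asks subjects to report respiratory illness or ILI symptoms.

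SAP 4.4 tabulates SAEs and NOCIs up to 30 days after Visit 4 or discontinuation. Later events are only listed.

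**The concern.** Three end points apply to the same primary outcomes: 15 May in the definition, Visit 4 for solicitation, and Visit 4 plus 30 days for the tables. For subjects vaccinated early they differ by weeks. In the last stretch of the stated window no scheduled contact asks about safety, and for part of it the events that do arrive are left out of the tables.

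The events most exposed are non-serious NOCIs diagnosed late. A hospital admission will often reach the site by itself. A new chronic diagnosis made in primary care may not, unless someone asks. A long NOCI window exists to catch such late diagnoses. The result would be absolute SAE and NOCI rates that are presented as covering a period they do not fully cover.

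**Working it through.** **Inputs**
- Dose 2: Day 22, window +9 days (Protocol 6.2, Tables 3 and 4).
- Visit 4: dose 2 + 180 days, ±14 (Protocol 7.4).
- End of outcome window: 15 May 2019 (Cohort 1) and 15 May 2020 (Cohort 2), Protocol 7.3 and 7.5.
- Table cut-off: Visit 4 + 30 days (SAP 4.4).
- Dose dates: not stated, so those used below are assumptions. There are two anchors. SAP 3.4 puts dosing before the influenza season. Protocol Table 3 starts Cohort 1 swabbing on 15 September 2018, with swabs taken from Day 14 after dose 2. This suggests, but does not prove, second doses from about 1 September 2018.

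**The plan's own figure.** Day 22 + 180 = Day 202, as stated for Visit 4.

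**When Visit 4 precedes 15 May**
- Nominal: dose 2 before 15 May − 180 days, which is 16 November 2018 (17 November 2019 for Cohort 2). Taking off a further 22 days gives a first dose before 25 October 2018 (26 October 2019).
- Both visits at the late end of their windows: 31 + 180 + 14 = 225 days from first dose, and 15 May 2019 − 225 days = 2 October 2018. A first dose before that date leaves a gap even when both visits are as late as allowed.

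**Size of the gap (Cohort 1).** Gap = 15 May − (dose 2 + 180), with ±14 for the visit window. Share = gap / (202 + gap), taking first dose 22 days before dose 2. Not tabulated = gap − 30, if positive.

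| Assumed dose 2 | Visit 4 | Gap, days (window) | Share of outcome window | Visit 4 + 30 | Days not tabulated |
|---|---|---|---|---|---|
| 1 Sep 2018 | 28 Feb 2019 | 76 (62–90) | 76/278 = 27% | 30 Mar 2019 | 46 |
| 1 Oct 2018 | 30 Mar 2019 | 46 (32–60) | 46/248 = 19% | 29 Apr 2019 | 16 |
| 1 Nov 2018 | 30 Apr 2019 | 15 (1–29) | 15/217 = 7% | 30 May 2019 | 0 |

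Cohort 2 gaps are one day longer because 2020 is a leap year.

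**When the SAP tables reach 15 May.** 15 May − 210 days gives a second dose on or after 17 October 2018 (18 October 2019) at nominal timing.

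**Other contacts in the gap.** The active calls ask about ILI. Under the protocol they end on 31 March, leaving 45 days to 15 May with no routine outgoing call. SAP 5.1 runs them to the week of 30 April for Cohort 2, leaving about 15 days, and allows extension for Cohort 1. The early termination visit (Protocol 7.7) is for subjects who withdraw or are withdrawn or terminated. None of these supplies a scheduled SAE/NOCI question at the end of the window for subjects who complete.

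**The case against.** The best defence is that collection never stops. Protocol 7.3 and 9.3 keep SAE and NOCI recording open to the end of participation, SAEs go in within 24 hours of site awareness, and suspected related SAEs are reportable even after the study. Six months of solicited follow-up after the last dose, with reporting thereafter, is a legitimate design. Frequent ILI calls keep subjects in touch through much of the gap, and a serious event could surface in one. All of this stands, and it means the defect is uneven ascertainment and not a missing collection rule. It does not supply a question about non-serious NOCIs.

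A reader might infer that the gap biases the comparison between arms. The documents do not support that. Randomisation is 1:1, central and stratified by cohort, assessors are blinded, and the same schedule applies to both arms.

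A reader might also infer that rates by season are not comparable. The SAP cut-off limits this: at nominal timing the tabulated tail is the same 30 days for everyone first dosed before about 25 September 2018 (17 October less 22 days). No between-season safety test is planned, and the documents do not show whether enrolment timing differed between seasons.

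Nor does every first dose before 25 October leave a gap, because the visit windows can close it for first doses from 2 October 2018 onward.

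The SAP already separates late events from the tables. That reduces the practical effect, but it is also what leaves the tables short of the outcome window that the SAP itself defines.

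**Conclusion.** The point holds as an inconsistency with a moderate consequence. For subjects vaccinated well before the season, part of a primary safety window is not solicited, and a smaller part is not tabulated either. On assumed second doses of 1 September and 1 October 2018 the unsolicited part is 76 days (62–90) and 46 days (32–60), and the untabulated part is 46 and 16 days at nominal timing. How many subjects are affected cannot be worked out, because dose dates are not given. The figures also assume that surveillance ends on 15 May as scheduled.

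The expected effect is under-recording of late events in both arms alike, chiefly non-serious NOCIs. Absolute rates would be somewhat low for the stated window, and sensitivity to a late signal would be reduced. It is worth correcting because it touches primary outcomes and the correction is cheap.

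**What to change.** Reconcile the outcome window (Protocol 3.2.1, SAP 3.1) with the timing of Visit 4 (Protocol 7.4, Tables 3 and 4) and the table cut-off (SAP 4.4). There are two ways.

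1. For Cohort 2, add one closing phone or e-mail contact at the end of passive surveillance, using the Visit 4 SAE/NOCI questions, for subjects whose Visit 4 came earlier. Extend the SAP tables to that date. The cost is one short contact per affected subject, out of about 8,000 planned in that cohort; this is small beside calls of up to twice a week. Cohort 1 cannot realistically be included: protocol version 5.0 is dated 8 May 2019, a week before that cohort's participation ends. Solicitation would then differ between cohorts, and the report should say so.

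2. For both cohorts, state that solicited SAE/NOCI ascertainment ends at Visit 4, make Visit 4 the common cut-off for the primary SAE/NOCI comparison, and tabulate later events to 15 May separately by arm. This costs wording and an extra set of tables. Its drawback is a primary safety window that is shorter than now stated for subjects vaccinated early.

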7.7. Early Termination Visit

The following activities will be performed at the early termination visit for subjects who withdraw, or are withdrawn or terminated from the study:

- Obtain interim medical history by interview of subjects and note any changes since the previous visit.
- Memory aid information will be reviewed with subjects (if within 22 days after the last study vaccination, day of the vaccination inclusive).
- If indicated by medical history, perform physical examination and/or obtain vital signs including oral temperature. Subjects must not eat or drink anything hot or cold, or smoke within 10 minutes prior to taking oral temperature.
- Review and record all concomitant medications (if within 22 days after the last study vaccination, day of the vaccination inclusive).
- Information regarding reactions recorded in diary/-ies, AEs and SAEs will be recorded on the appropriate data collection form. Recording of AEs in the EDC will be limited to SAEs if after 21 days following the last study vaccination day.

- Examine study vaccination site, and perform post- administration reactogenicity assessment (if within 8 days after the last study vaccination, day of the vaccination inclusive).

7.8. **Unscheduled Visit**

Unscheduled visits may occur at any time during the study. Any of the following activities may be performed:

- Review memory aid (if within 22 days after the last study vaccination day, inclusive of the vaccination day).
- Review and record all concomitant medications (if within 22 days after the last study vaccination day, inclusive of the vaccination day).
- All reactions recorded in diary/-ies, AEs, SAEs will be recorded on the appropriate data collection form. Recording of AEs in the EDC will be limited to SAEs if after 21 days after the last study vaccination day.
- Obtain interim medical history by interview of subjects and note any changes since the previous visit (if indicated).
- If deemed as relevant and/or needed, perform physical examination and/or obtain vital signs including oral temperature. Subjects must not eat or drink anything hot or cold, or smoke within 10 minutes prior to taking oral temperature.
- Examine study vaccination site and perform post- administration reactogenicity assessment (if within 8 days after the last study vaccination, inclusive of vaccination day).

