5.3.3. Reasons for Withdrawal

Subjects may voluntarily withdraw their consent for study participation at any time and for any reason, without penalty.

A subject may withdraw or be withdrawn from the study for any of the following reasons:

- Medical disease or condition, or any new clinical findings for which continued participation, in the opinion of the site PI or appropriate SI, would compromise the safety of the subject, or would interfere with the subject's successful completion of the study, or would interfere with the evaluation of responses.
- Subject no longer meets eligibility criteria.
- As deemed necessary by the site PI or appropriate SI for noncompliance or other reasons.
- Subject withdrawal of consent.
- Subject lost to follow-up.
- Termination of the study or the study cohort.
- New information becomes available that makes further participation unsafe.

Subsequent study vaccinations will not be administered to a subject if any of the following criteria are met:

- Medical condition for which continued participation, in the opinion of the site PI or appropriate SI, would pose a risk to the subject or would be likely to confound interpretation of the results.

- Presence of signs or symptoms that could confound or confuse assessment of study vaccine reactogenicity. For subjects with injection site or systemic signs or symptoms, or with an acute illness, the subsequent study vaccinations should be postponed/deferred until signs, symptoms, or acute illness have sufficiently resolved as per PI/SI judgment, and if within the expected protocol-specified window for that visit. If outside this window, the PI must first obtain approval for the second study vaccination from the study sponsor and the documentation of the approval should be filed in the subject's file.
- Any unresolved by or continuing at Visit 2 Grade 3 AE. An unresolved or continuing Grade 1 or 2 AE (grade 2 except for temperature which at grade 2 is not acceptable for vaccination) is permissible unless, in the opinion of the PI or SI, it would render study vaccination unsafe or interfere with the evaluation of responses.
- Solicited reactogenicity event grade 3 or AE grade 3 AE, within the 8 days following study vaccination (day of the vaccination inclusive), that has no alternative (to the vaccination) etiology.
- Subject no longer meets eligibility criteria.
- As deemed necessary by the site PI or appropriate SI for noncompliance or other reasons.

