Adverse events of special interest (AESIs) will be captured as SAEs and within the same timelines throughout the subject's participation in the trial. These include new onset of Guillain-Barré Syndrome (GBS), Bell's Palsy, encephalitis / myelitis, optic neuritis, Stevens-Johnson Syndrome, and toxic epidermal necrolysis.

NOCIs should be collected from the time of the first study vaccination throughout the subject's participation in the trial. NOCI is defined as diagnosis of a chronic medical condition where the symptoms commenced or worsened following exposure to the study vaccine. NOCIs meeting criteria of SAE will be recorded as SAE.

Events classified as ILI will not be recorded as AEs/SAEs unless they occur during period from first or second vaccination within 8 days (the vaccination day inclusive) post the respective vaccination or if they meet seriousness criteria - then they are also (in addition to being reported as ILI) reported as SAEs, because ILI cases are to be recorded separately and analyzed for efficacy assessment.

Severity of Event: AEs will be assessed by a licensed study physician using a protocol-defined grading system (see section 9.2.2). For events not included in the protocol-defined grading system, the following guidelines will be used by PI/SI to quantify severity, taking into account subject's medical history, concomitant medications, and baseline values:

- Mild (Grade 1): Events require minimal or no treatment and do not interfere with the subject's daily activities.
- Moderate (Grade 2): Events result in a low level of inconvenience or concern with therapeutic measures. Moderate events may cause some interference with functioning and daily activities.
- Severe (Grade 3): Events interrupt the subject's usual daily activities and may require systemic drug therapy or other treatment. Severe events are usually incapacitating.

Relationship to Study Product: The study physician's assessment of an AE's relationship to study product is part of the documentation process, but it is not a factor in determining what is or is not

reported in the study. If there is any doubt as to whether a clinical observation is an AE, the event should be reported. The relationship to study product must be assessed for AEs using the terms: none, unlikely, possible, probable, certain. In a clinical trial, the study product should be considered as potential suspect. To help assess, the following guidelines are used:

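### Protocol 7.7 and 7.8 limit late EDC entry to SAEs, contradicting the rules that non-serious new-onset chronic illness, a primary safety outcome, is recorded throughout participation

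*Protocol*

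**What the plan says.** Protocol 7.7 (early termination) and 7.8 (unscheduled visit) carry almost the same sentence. In 7.7 it reads "Recording of AEs in the EDC will be limited to SAEs if after 21 days following the last study vaccination day"; in 7.8, "Recording of AEs in the EDC will be limited to SAEs if after 21 days after the last study vaccination day". Neither section mentions NOCIs.

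The primary safety outcomes in Protocol 3.2.1 include "Occurrence of NOCIs from the time of the first study vaccination (M-001 or placebo) until end of first passive surveillance period". Protocol 9.2.1 says "NOCIs should be collected from the time of the first study vaccination throughout the" subject's participation, and adds that a NOCI is recorded as an SAE only if it meets SAE criteria. Sections 7.3 and 9.3 set the same collection period. For the Visit 4 contact, Protocol 7.4 says "AEs limited to NOCIs and SAEs that have occurred since the previous visit will be solicited".

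SAP 4.4 tabulates NOCIs whether serious or not, from first vaccination to 30 days after Visit 4 or after discontinuation. It therefore expects NOCIs from subjects who left early.

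**The concern.** A non-serious NOCI is by definition not an SAE, so it is the kind of event that the two visit-level sentences leave out after the cut-off. These sentences are the only text that says what enters the EDC at those two visits. Site staff following them and site staff following 9.2.1 would act differently on the same diagnosis.

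At stake is the completeness of a primary safety outcome. The SAP summarises NOCIs from the database, and three of its four NOCI tables are marked for the top-line results (SAP 12). Its missing-data rules cover missing severity, causality and dates. No analysis rule can restore an event that was never entered.

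**Working it through.** No statistical figure is in question. The check compares the collection rules and then does the day arithmetic.

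**1. Does the sentence in 7.7 and 7.8 reach NOCIs?** Yes, on the protocol's own usage. Section 7.4 treats NOCIs as a kind of AE (AEs limited to NOCIs and SAEs). Section 9.3 has to exclude NOCIs expressly from non-serious unsolicited AEs, which implies that they would otherwise be included. A limit on AEs to SAEs alone therefore leaves out a non-serious NOCI.

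**2. What do the other sections require?**

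| Place | Rule for a non-serious NOCI more than 21 days after the last dose |
|---|---|
| 3.2.1 | Inside the primary outcome window |
| 7.3 | Collected from Day 0 to the end of participation |
| 7.4 (Visit 4) | Solicited |
| 9.2.1 | Exempt from the roughly 22-day eCRF limit; collected throughout participation |
| 9.3 | Exempt from the 22-day limit; documented through participation |
| Tables 3 and 4 | Collected at any time in the study |
| SAP 4.4 | Tabulated |
| **7.7 and 7.8** | **Not entered in the EDC** |

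**3. When does the limit start?** It counts from the last vaccination, not from study Day 0.

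- Two doses on schedule: Day 22 + 21 = Day 43, so it applies from Day 44.
- Second dose at the end of the +9 window (Day 31): 31 + 21 = Day 52, so it applies from Day 53.
- One dose only (Day 0): it applies from Day 22.

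**4. How long does it last?** Visit 4 is on Day 22 + 180 = Day 202, which matches the schedule. Days 44 to 202 inclusive are 202 − 44 + 1 = 159 days, or 159/180 = 88% of the 180 days after the second dose. This is a share of calendar time, not of NOCIs.

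**5. Would a later contact recover the event?**

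- *Early termination:* the visit may be the last contact, in which case there is no Visit 4.
- *Unscheduled visit:* the subject stays in the study and Visit 4 follows. However, Visit 4 asks about events since the previous visit. If the unscheduled visit counts as that visit, the NOCI may not be asked about again.
- *After Visit 4:* the outcome window runs to the end of passive surveillance on 15 May. Since 15 May 2020 minus 180 days is 17 November 2019, a last dose before that date puts the nominal Visit 4 before the window closes. Table 4 schedules no later safety visit.
- *Medication prompt:* Protocol 6.5 uses new medication to prompt a check for new chronic disease, but 7.7 and 7.8 limit medication review to 22 days after the last dose.

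**The case against.** The strongest reply is that the protocol's intent is clear and 7.7 and 7.8 are outliers. Sections 7.3, 9.2.1, 9.3 and both schedules agree, so a site reading the whole protocol would enter the NOCI. Even at the early-termination visit the event is not missed at source: the site must "Obtain interim medical history by interview of subjects and note any changes since the previous visit", and "AEs and SAEs will be recorded on the appropriate data collection form" without a time limit in that sentence. Monitors compare eCRF entries with source (Protocol 10.1). Vaccinated subjects are encouraged to stay for safety follow-up, and AEs ongoing at withdrawal are followed (Protocol 5.3.4).

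Most of this stands, and it rules out several stronger readings that a reader might infer:

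- *That these NOCIs are lost.* The documents support possible under-entry at some sites, not certain loss.
- *That the limit starts on study Day 21.* For two-dose subjects it starts at about Day 44.
- *That these visits are where NOCIs are most likely to appear.* Nothing in the documents says so; Visit 4 is the planned contact that solicits them.
- *That about 1,200 subjects are affected (10% of 12,000).* The 10% in Protocol 11.3 combines loss to follow-up with per-protocol exclusion. It is not a count of early terminators.
- *That the under-entry is informative.* Section 5.3.3 does list new medical conditions and "Subject no longer meets eligibility criteria" as reasons for withdrawal. But withdrawal is permissive, a diagnosis meeting exclusion criterion 4 may qualify as an SAE and be entered anyway, and staff assessing safety are blinded. Informative loss is possible but not shown.

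What the reply does not remove is the contradiction. Form-level capture makes an omission traceable only if someone looks for it, and a monitor applying 7.7 literally would see no discrepancy. Following an ongoing AE after withdrawal does not itself say that the event enters the EDC.

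**Conclusion.** This is an internal inconsistency that is wrong as written, of low to moderate severity. More than 21 days after the last dose, 7.7 and 7.8 on their face keep a non-serious NOCI out of the EDC, while 7.3, 9.2.1 and 9.3 require it to be recorded. The consequence is possible under-recording of a primary safety outcome, mainly at early-termination visits that turn out to be the last contact.

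The 159-day figure assumes two doses on schedule and counts to the nominal Visit 4. The number of NOCIs affected cannot be estimated: the documents give no rate for NOCIs, early termination or unscheduled visits. No difference between arms is shown. Confidence is high on the wording conflict and limited on its practical effect, which depends on which section sites followed.

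**What to change.** In both 7.7 and 7.8, change the limit on late EDC recording from SAEs to SAEs and NOCIs, to agree with 7.3, 7.4, 9.2.1 and 9.3. AESIs need not be added, because they are already captured as SAEs.

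Before database lock, check source notes and data collection forms from early-termination and unscheduled visits held more than 21 days after the last dose, and enter any NOCI found there but not in the EDC.

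The cost is two sentences in the protocol, a matching note in the eCRF completion guidelines and a one-off source check. Endpoints, sample size and planned analyses do not change.
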